#### **7.2.1.2 Medication and Medical History**

##### **Medication History**

Refer to Section [5](#) for full details on collection of prior treatment.

The investigator will categorize treatments as ocular (specified as left eye, right eye or both eyes) or non-ocular based on the indication for use. Prior treatment information must be recorded on the appropriate CRF page.

### **Medical History**

The site must record all clinically or medically relevant information regardless of how much time has elapsed since the date of any diagnosis. Medical history will be classified as ocular (specified as left eye, right eye or both eyes) or non-ocular by the investigator. History should include, but is not limited to:

- History of ocular diseases/conditions.
- History of respiratory, cardiovascular, renal, gastrointestinal, hepatic, endocrine, hematological, neurological, and any other non-ocular diseases/underlying conditions within the past year prior to the Screening Visit (Visit 1).

#### **7.2.1.3 AdenoPlus Test**

The AdenoPlus test will be performed at Visit 1 as outlined in [Table 1](#). A positive result in at least one eye is required for enrollment in this study (unless at least 2 of the 5 criteria from Inclusion Criteria 4b, based upon medical history and examination, are met).

The AdenoPlus test is an in-office test that allows for the detection of adenoviral antigens directly from human eye fluid. A small tear sample is transferred onto the AdenoPlus test, which confirms the presence of adenovirus and the viral form of conjunctivitis.

Please refer to the Study Operations Manual for a detailed description of the AdenoPlus Test and administration.

### **7.2.2 Efficacy**

#### **7.2.2.1 Clinical Resolution**

Clinical resolution of adenoviral conjunctivitis is defined as the absence (score = 0) of bulbar conjunctival injection and watery conjunctival discharge in the study eye. Bulbar Conjunctival Injection will be assessed based on a 0-4 scale which uses pictures from the Validated Bulbar Redness (VBR) Scale and Watery Conjunctival Discharge will be assessed based on a 0-3 scale. Details of the Bulbar Conjunctival Injection and Watery Conjunctival Discharge scales are located in the Study Operations Manual.

#### **7.2.2.2 Adenoviral Eradication**

Adenoviral eradication for an eye is defined as negative CC-IFA in that eye. CC-IFA for each eye will be conducted using conjunctival swab samples collected at each visit. See the Laboratory Manual for further details.

### 7.2.3 Safety

Safety assessments will be performed in both eyes.

#### 7.2.3.1 Best Corrected Visual Acuity (BCVA)

The BCVA will be performed prior to slit lamp examination during the study as outlined in [Table 1](#).

The complete instructions for performing the BCVA are in the Study Operations Manual. Changes in VA will be assessed for clinical significance. Clinically significant changes should be recorded in the source and on the eCRF as an AE.

For subjects who are too young to use an ETDRS chart, use an age-appropriate measurement method in accordance with the AAP Policy Statement for Visual System Assessment in Infants, Children, and Young Adults by Pediatricians ([Donahue and Baker, 2016](#); [American Academy of Pediatrics, 2016](#); located in the Study Operations Manual). The policy statement recommends formal vision screening can begin at 3 years of age. VA measurements for children under the age of 3 will be done at the discretion of the investigator. If not done, child should be able to fixate on and follow a moving object. This is not a requirement in subjects <2 months of age since the ability does not develop until about 2 months of age. However, if an infant <2 months of age is able to fix and follow, it should be recorded. The enrollment of subjects <2 months of age will be based on subject qualifying all other eligibility criteria and investigator discretion.

VA is to be measured using the same method at all visits in the same subject.

#### 7.2.3.2 Slit Lamp Biomicroscopy

Slit lamp biomicroscopy (or hand held slit lamp) will be performed during the study as outlined in [Table 1](#). Magnification of the slit lamp will be consistent with standard clinical practice. The subject will be seated.

Observations will be graded as Normal or Abnormal. Abnormal findings will be described, and clinically significant abnormalities should be recorded in the source and on the electronic CRF (eCRF) (in Medical History at Screening; any changes from the screening visit may be recorded as adverse events by the investigator). Please note the investigator may use his/her discretion to determine whether Not Clinically Significant (NCS) and disease progression should be considered AEs). The following will be examined at each visit:

- Lids
- Conjunctiva
- Cornea
- Anterior Chamber
- Iris

- Lens

For infants and young children, if the above exams cannot be performed with a slit lamp or a hand held slit lamp, an external examination is to be conducted in accordance with American Academy of Pediatrics (AAP) Policy Statement for Visual System Assessment in Infants, Children, and Young Adults by Pediatricians ([Donahue and Baker, 2016](#); [American Academy of Pediatrics, 2016](#); located in the Study Operations Manual). The examination of lens in these subjects should be conducted at Visit 1 and Visit 5 (or ET visit) and graded based on the external examination and red reflex exam (Section [7.2.3.4](#)). All other structures listed above will be examined and graded at all visits based on the external examination. Observations will be graded as Normal or Abnormal. Abnormal findings will be described.

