## 8. ADVERSE AND SERIOUS ADVERSE EVENTS ASSESSMENT

### 8.1 Definition of Adverse Events, Period of Observation, Recording of Adverse Events

An AE is any untoward medical occurrence in a clinical investigation subject administered a pharmaceutical product and that does not necessarily have a causal relationship with this treatment. An AE can therefore be any unfavorable and unintended sign (including an abnormal laboratory finding), symptom, or disease temporally associated with the use of a medicinal (investigational) product, whether or not related to the medicinal (investigational) product (ICH Guidance E2A 1995).

All AEs are collected from the time the informed consent is signed until the defined follow-up period stated in Section 7.1.3. This includes events occurring during the screening phase of the study, regardless of whether or not investigational product is administered. Where possible, a diagnosis rather than a list of symptoms should be recorded. If a diagnosis has not been made, then each symptom should be listed individually. All AEs should be captured on the appropriate AE pages in the CRF and in source documents. In addition to untoward AEs, unexpected benefits outside the investigational product indication should also be captured on the AE CRF.

All AEs must be followed to closure (the subject's health has returned to his/her baseline status or all variables have returned to normal), regardless of whether the subject is still participating in the study. Closure indicates that an outcome is reached, stabilization achieved (the investigator does not expect any further improvement or worsening of the event), or the event is otherwise explained. When appropriate, medical tests and examinations are performed so that resolution of event(s) can be documented.

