#### **8.1.4 Symptoms of the Disease Under Study**

Symptoms of the disease under study should not be classed as AEs as long as they are within the normal day-to-day fluctuation or expected progression of the disease and are part of the efficacy data to be collected in the study; however, significant worsening of the symptoms should be recorded as an AE.

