^g If a non-dilated fundus exam is not feasible, a dilated examination should be conducted. For each subject the exam should be conducted the same way (either non-dilated or dilated) at both Visit 1 and Visit 5 (or ET).

^h All assessments, randomization, and investigational product instillation on Day 1 must take place with sufficient time to allow all 4 Day 1 doses (with a minimum of 2 hours between doses).

ⁱ The investigational product bottle should be shaken well prior to use at each dosing. The first dose will be administered by site staff on Day 1, and thereafter subjects will administer 1 drop in each eye 4 times a day for 7 days.

^j Investigational product instillation should only be performed in-office if it is necessary.

^k Monitoring for adverse events will begin after informed consent is obtained. Information about AEs unresolved at the time of study exit (eg, resolution status, resolution date, treatment received for AE) and related information (eg, data from any assessments conducted to follow up on the status of unresolved AE) for a period of up to 14 days after subject exit may be collected by the Sponsor. Corneal AEs that are ongoing at the end of study visit should be followed up by the site until resolution or stabilization and all related information should be collected in the CRF.

^l This sample will be used for baseline HSV testing for all subjects. For subjects <2 months of age, testing will also be conducted using the same sample for chlamydia and gonorrhea detection.

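### Protocol 7.2.3.2 leaves AE recording of slit-lamp changes to the investigator, so a clinically significant new corneal finding judged to be disease progression can miss the TEAE tables and the AE-only follow-up rule

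*Protocol*

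**What the plan says.** **Recording rules in the protocol (Amendment 4).**
- Section 7.2.3.2 (slit lamp) sends clinically significant abnormalities to the source and the eCRF. Its parenthesis places them in medical history at screening and, after that, says "any changes from the screening visit may be recorded as adverse events by the investigator". It then adds that "the investigator may use his/her discretion to determine whether Not Clinically Significant (NCS) and disease progression should be considered AEs".
- Section 7.2.3.1 (visual acuity) says: "Clinically significant changes should be recorded in the source and on the eCRF as an AE". Section 7.2.3.4 (fundus) uses the same sentence.
- Section 8.1 counts any unfavourable and unintended sign as an AE and says: "All AEs should be captured on the appropriate AE pages in the CRF and in source documents".
- Section 8.1.4 keeps disease symptoms off the AE page only while they stay within their expected course and "are part of the efficacy data to be collected in the study; however, significant worsening of the symptoms should be recorded as an AE".

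**Follow-up.** Sections 7.1.3 and 8.1 require AEs to be followed to closure. Section 7.1.4 plans no aftercare. SAP 2.4, footnote k, adds: "Corneal AEs that are ongoing at the end of study visit should be followed up by the site until resolution or stabilization".

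**Reporting.** The TEAE tables in SAP 11.1 are built from recorded AEs. SAP 11.2 and Table 14.3.6.2 summarise the cornea by visit, eye and arm in three grades (normal, abnormal but not clinically significant, abnormal and clinically significant). Listing 16.2.8.2 gives slit-lamp results by subject. Under SAP 18.4, unscheduled exams are left out of by-visit tables but kept in listings.

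**The concern.** The documents themselves treat the cornea as important. Exclusions 8, 9 and 18 bar corneal inflammation, subepithelial infiltrates, epithelial defects and significant opacity at entry. Section 1.1 mentions permanent visual compromise from immune-mediated sequelae. Yet the slit lamp, which is the examination that grades the cornea, has the loosest AE-recording rule of the three eye examinations compared here.

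If two sites read the discretion differently, the corneal TEAE counts partly reflect site habit. A finding that never becomes an AE also falls outside the only written follow-up duty. SAP section 17 makes this weigh more: after early termination the abbreviated report gives efficacy in brief but promises full safety information, so the safety tables are the main output.

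**Working it through.** The point rests on wording, and the plan states no figure to reproduce. The check sets the rules side by side and then traces one case.

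**1. The rules compared**

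| Section | What it covers | Instruction on AE entry |
|---|---|---|
| 7.2.3.1 Visual acuity | clinically significant changes | should |
| 7.2.3.4 Fundus | clinically significant changes | should |
| 7.2.3.2 Slit lamp | any change from screening | may |
| 7.2.3.2 Slit lamp | findings not clinically significant; disease progression | investigator's discretion |
| 8.1 | any unfavourable, unintended sign | should be captured |
| 8.1.4 | expected disease symptoms that are also efficacy data | exempt unless significantly worse |

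**2. Are corneal findings efficacy data?** The primary, key secondary and secondary endpoints in 9.8.2 to 9.8.4 use bulbar injection, watery discharge, CC-IFA and qPCR. Slit-lamp results, including the cornea, sit under safety in 7.2.3 and 9.9. The exploratory endpoints are not legible in the public copy. However, SAP section 10 says all efficacy endpoints will be listed, and none of the listings grouped as 16.2.6.1 to 16.2.6.6 is corneal. So 8.1.4 gives no exemption for a corneal finding.

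**3. One case traced.** Take a new subepithelial infiltrate at Visit 4, graded clinically significant and judged by the investigator to be disease progression.
- Under 7.2.3.2 it goes to the source and eCRF, and AE entry is optional.
- Under 8.1 it is an unfavourable sign and should be an AE. Under 8.1.4 it is not exempt. These two sections and 7.2.3.2 give different answers.
- If the site follows 7.2.3.2 and makes no AE entry, the finding is in no TEAE table (SAP 11.1), and the closure rule of 7.1.3 and 8.1 does not apply.
- It does appear in Table 14.3.6.2 at Visit 4 and in Listing 16.2.8.2. Had it been seen only at an unscheduled exam, it would be in the listing alone.

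**4. What the by-visit table can show.** SAP 11.2 specifies change from baseline for visual acuity and intraocular pressure but not for the slit lamp. Let n(v,e) be the number of subjects in an arm with a clinically significant corneal grade at scheduled post-baseline visit v in eye e. The number with such a grade at any scheduled visit in either eye lies between the largest n(v,e) and the sum of all n(v,e). Subjects seen only at unscheduled exams come on top. The table therefore brackets the cumulative count but does not give it. The count can be built from the subject-level data, but no planned table does so.

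**5. Direction of any effect.** Suppose a fraction q of such findings is entered as AEs, the same in both masked arms, and the true proportions are p1 and p2. The tables then show q·p1 and q·p2. The difference becomes q(p1 − p2), and the expected ratio stays p1/p2. The documents give neither q nor p1 or p2.

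**The case against.** The case against has four parts.

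- **The contrast is not like for like.** *May* attaches to any change, including trivial ones, while *should* in the other two sections covers only clinically significant changes. Since 7.2.3.2 names only non-significant findings and disease progression as discretionary, a clinically significant change that is not progression is arguably meant to be an AE. This is a fair reading and it narrows the gap to disease progression. It does not close it: that term is undefined, and the only sentence about AE entry after screening still says *may*.
- **The general rules already cover the case.** 8.1 and the worsening clause of 8.1.4 do point that way. But 7.2.3.5 says AEs may be determined during examinations as described in the preceding sections, which sends the site back to 7.2.3.2. The sections conflict, and none is said to prevail.
- **Versions are mixed.** The SAP follows Amendment 5, while the slit-lamp text is from Amendment 4, whose own AE footnote has no corneal clause. A reader might infer from SAP footnote k that the same protocol version sets a special corneal follow-up and then undercuts it. The documents supplied cannot show that. The point rests on the closure rule in 7.1.3 and 8.1, which is in Amendment 4.
- **Nothing is lost from the data.** A reader might infer that new corneal findings vanish from the safety report or cannot be counted. They do not vanish: the listing holds every exam. And because exclusions 8, 9 and 18 remove most corneal disease at entry, most clinically significant grades after baseline should be new. Only a cumulative count per subject is missing.

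It is also true that amending the protocol cannot change AE data already collected in a terminated trial.

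**Conclusion.** The point holds in limited form. As written, 7.2.3.2 conflicts with 8.1 and 8.1.4 and is looser than 7.2.3.1 and 7.2.3.4. It allows a clinically significant new corneal finding, judged to be disease progression, to stay outside the TEAE tables and the AE-only closure rule.

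A reader might go further and infer a known shortfall in corneal TEAEs, or that affected subjects were in fact left without follow-up. Neither is supported. No corneal event rate or recording fraction is given, and the absence of a written duty does not show what investigators did. With equal recording in both arms, an assumption that cannot be tested here, under-recording would shrink an absolute difference but not the expected ratio.

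The conclusion assumes that the slit-lamp wording of Amendment 4 governed recording. Amendment 5, the CRF Completion Guidelines and the Study Operations Manual are not available and may have settled the matter.

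**What to change.** **Protocol.** Check the Amendment 5 text of 7.2.3.2 first. If it is unchanged, reconcile it with 8.1 and 8.1.4: use the sentence of 7.2.3.1 and 7.2.3.4 for clinically significant changes from Visit 1, and limit the discretion to findings that are not clinically significant and to disease signs that are efficacy data.

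**SAP.** AE recording may no longer be open to change, so add one row per arm to SAP 11.2 and Table 14.3.6.2. It counts subjects whose cornea was normal or abnormal but not clinically significant at baseline, and abnormal and clinically significant at any later exam in the same eye, for either eye, including unscheduled exams. This does not depend on AE entry and stays feasible after early termination.

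**Cost.** A few more AE entries in both arms if recording is still open, and one derived row from grades already collected. The row needs a stated exception to SAP 18.4, which otherwise excludes unscheduled exams from the by-visit tables.

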### **7.2.3.3     Intraocular Pressure**

At Visit 1 and Visit 5 (or Early Termination visit), IOP will be assessed in both eyes using either Goldmann tonometer or a Tono-pen®. The same method of measurement must be used for each patient throughout the entire time of participation in the study. For both methods (Goldmann and Tono-Pen®), sterile disposable single-use tips must be used each time to prevent cross-contamination. Other measures as appropriate should be taken to prevent cross-contamination. For children <12 years of age, all efforts should be made to obtain IOP by an appropriate method (e.g., I-Care can be used for children <12 years of age).

### **7.2.3.4     Non-dilated/Dilated Fundus Examination**

Fundus examination must be conducted after BCVA, Slit Lamp Biomicroscopy and conjunctival swab for adenoviral and bacterial culture has been collected.

A non-dilated fundus examination will be performed in all subjects with the exception of infants and uncooperative small children during the study as outlined in [Table 1](#).

Observations will be graded as Normal or Abnormal. Abnormal findings will be described.

The following will be examined:

- Vitreous
- Optic Nerve
- Macula

Clinically significant changes should be recorded in the source and on the eCRF as an AE.

If a non-dilated fundus exam is attempted and is not feasible, dilated fundus exam should be conducted. The test should be conducted the same way (either dilated or non-dilated) at both Visit 1 and Visit 5 (or ET).

For infants and small children in whom a fundus examination cannot be done, a red reflex exam will be conducted in accordance with AAP Policy Statement for Visual System Assessment in Infants, Children, and Young Adults by Pediatricians ([Donahue and Baker, 2016](#); [American Academy of Pediatrics, 2016](#); located in the Study Operations Manual). Observations will be graded as Normal or Abnormal. Abnormal findings will be described. The red reflex should be normal (present and symmetrical for both eyes) at the screening/ baseline visit.

#### **7.2.3.5 Adverse Event Collection**

At each study visit, subjects will be questioned in a general way to ascertain if AEs have occurred since the previous visit (eg, “Have you had any health problems since your last visit?”). Adverse events are collected from the time informed consent is signed. (Please refer to Section 8, Adverse and Serious Adverse Events Assessment.) Any AE that occurs after the first dose of investigational product instillation will be considered a TEAE.

Adverse events may also be determined by the investigator during study examinations as mentioned in previous sections.

#### **7.2.3.6 Microbiology Laboratory Evaluations**

All laboratory assays will be performed according to the laboratory’s normal procedures.

All bioanalytical assays for the study will be validated following FDA/ICH guidelines, based on the method’s intended use. The lab will only receive sample ID numbers and collection dates, the lab results will then be transferred to the central lab for data analysis. The lab will not receive any information on subject treatment assignment.

The following laboratory assessments will be performed:

- Cell Culture Assay (CC-IFA): This test will be performed on samples collected at all visits to determine the presence of adenovirus.
- quantitative Polymerase Chain Reaction (qPCR): This test will be performed on all CC-IFA positive samples at all visits to determine viral count.
- Adenoviral serotyping: This test will be done at baseline only to determine what serotypes of adenovirus are present.
- qPCR: This test will be performed on samples for qualitative detection of HSV at baseline (Visit 1).

One swab sample from each eye will be taken from inferior conjunctival cul-de-sac at all study visits for adenoviral testing. For neonates and infants <2 months of age, PCR testing for qualitative detection of chlamydia and gonorrhea at baseline will also be conducted using the baseline visit sample. Qualitative PCR: This test will be performed on samples from baseline visit (Visit 1) for HSV testing.

#### **7.2.3.7      Pregnancy Test**

A urine pregnancy test is performed on all females of childbearing potential at Visit 1 and Visit 5, or if pregnancy is suspected. Urine pregnancy test kits will be provided by the sponsor and read on site by qualified site personnel.

#### **7.2.3.8      Health-related Quality of Life Assessments**

Ocular discomfort associated with conjunctivitis symptoms will be assessed through the Ocular Discomfort Scale. The Ocular Discomfort Scale is composed of three items: pain, itching, and foreign body sensation. All items will be evaluated using a 0-10 scale. A separate scale will be administered for children less than 8 years of age (binary ocular discomfort). Please see the Study Operations Manual for a detailed description of this assessment.

## 8. ADVERSE AND SERIOUS ADVERSE EVENTS ASSESSMENT

### 8.1 Definition of Adverse Events, Period of Observation, Recording of Adverse Events

An AE is any untoward medical occurrence in a clinical investigation subject administered a pharmaceutical product and that does not necessarily have a causal relationship with this treatment. An AE can therefore be any unfavorable and unintended sign (including an abnormal laboratory finding), symptom, or disease temporally associated with the use of a medicinal (investigational) product, whether or not related to the medicinal (investigational) product (ICH Guidance E2A 1995).

All AEs are collected from the time the informed consent is signed until the defined follow-up period stated in Section 7.1.3. This includes events occurring during the screening phase of the study, regardless of whether or not investigational product is administered. Where possible, a diagnosis rather than a list of symptoms should be recorded. If a diagnosis has not been made, then each symptom should be listed individually. All AEs should be captured on the appropriate AE pages in the CRF and in source documents. In addition to untoward AEs, unexpected benefits outside the investigational product indication should also be captured on the AE CRF.

All AEs must be followed to closure (the subject's health has returned to his/her baseline status or all variables have returned to normal), regardless of whether the subject is still participating in the study. Closure indicates that an outcome is reached, stabilization achieved (the investigator does not expect any further improvement or worsening of the event), or the event is otherwise explained. When appropriate, medical tests and examinations are performed so that resolution of event(s) can be documented.

